**May 5th, 2024**

# PROTOCOL

## *General Procedures*

Participants completed three phases: Listening Session #1, Earmold Fabrication, and a Listening Session #2. See **Figure 4.2**. The primary distinction among listeners was the material-type of earmold they received first. There are three material-types and thus three groups that participants could be initially assigned to. All participants received and were tested with each of the three material-type groups. Earmolds were connected to the same Unitron T-Stride M behind-the-ear hearing aid.

**Figure 4. 1** Participant-study flow chart for RCT study.

## *Specific Procedures*

### Listening Session #01

[figure not shown]
Participants completed intake questionnaires that included questions about hearing health history, demographics, and study eligibility information. At this stage, researchers also informed participants of procedures, risks, and benefits of the study. If participants met eligibility criteria up to this point, they underwent conventional audiologic testing to evaluate hearing and ear function following best-practices for audiology. Otoscopy, a visual exam of the ear, was used to ensure patent ear canals, normal appearing tympanic membrane, and normally aerated middle

ear. Air conduction and bone conduction pure tone audiometry were used to establish hearing thresholds from 250 to 8000Hz, bilaterally. Normal hearing was considered thresholds equal or less than 25 dB HL. If participants met audiometric candidacy, a custom ear impression was made of one of their ears using a common, clinically used, two-part impression material.

## Randomization

Each participant was made three earmolds for a single ear. The main difference between participants was the material-type of earmold that they received first. All participants were eventually fit with and underwent testing with each earmold material-type. Participants were randomly assigned to one of three arms, using a 1:1 allocation ratio, each with a different initial material type. The three material-type groups included a control group (EMCTRL) made by a professional manufacturer, and two in-house study groups that were 3D printed using Resin (EMRES) and PLA (EMPLA). See **Figure 4.3**. Randomization was completed *a priori* via a list generated by a custom Microsoft Excel script. This script randomly sequenced three blocks of ten numbers equally containing values from 1 to 3. Once participants were deemed eligible, they were automatically assigned the next value on the randomized list, from 1 to 3, indicating which arm of the study they were allocated to.

**Figure 4.2** Workflow study diagram across material-type groups

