### Earmold Fabrication Period

After completing Listening Session #01, ear impressions were digitally scanned and edited using commercially available 3D editing software. The physical ear canal impression was then sent to a third-party earmold manufacturer. Each participant was made three earmolds, for an overall total of 90 earmolds. For each individual, one earmold was created using a *third-party* manufacturer with the traditional service delivery pathway and two earmolds were created *in-house* with the novel service-delivery pathway using local 3D printers. The *third-party* earmold served as the control earmold. The *in-house* earmolds were made from two different material-types and served as the study earmolds. To control for style of earmolds, all earmolds were made in a skeleton style with a sound bore that accommodates size #13T tubing and a separate select-a-vent (SAV).

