### Listening Session #02

Once all earmolds were fabricated and received, participants were scheduled for Listening Session #02. This stage involved collecting objective acoustic measurements and subjective perceptual ratings while wearing each of the earmolds. A stock Unitron T-stride M behind-the-ear hearing aid was programmed to simulate a flat, mild, sensorineural hearing loss at

40 dB HL from octave frequencies between 250 to 8000Hz. The hearing aid was programmed and fit to NAL-NL2 targets for these threshold values. All advanced hearing aid programming and features were disabled. The same hearing aid was used across all participants. Participants underwent objective and subjective measures three times, once for the *third-party* control earmold and twice for each *in-house* study earmold. Each material-type condition was separated by a short 10 minute washout period, during which participants completed a self-assessment questionnaire.

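### Only the first earmold is described as randomised; with one fixed order per arm, no set of three orders balances which material precedes which, so unequal carry-over could bias a pairwise material difference

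*Combined protocol and SAP*

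**What the plan says.** The Randomization section allocates by a single number: "Participants were randomly assigned to one of three arms, using a 1:1 allocation ratio, each with a different initial material type", and each eligible participant is "assigned the next value on the randomized list, from 1 to 3, indicating which arm of the study they were allocated to". It adds that "The main difference between participants was the material-type of earmold that they received first"; General Procedures says the same. The list is described thus: "This script randomly sequenced three blocks of ten numbers equally containing values from 1 to 3". No section describes a second allocation, or any counterbalancing, for the earmolds tested second and third. A workflow figure is cited, but it is not shown in the text available for this review.

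Listening Session #02 puts the three conditions one after another: "Participants underwent objective and subjective measures three times", and "Each material-type condition was separated by a short 10 minute washout period". Both acoustic measurements and perceptual ratings are collected. The Analysis Plan compares materials by a one-way within-participant RM-ANOVA and Bonferroni-corrected pairwise t-tests. It has no term for position, sequence or preceding earmold.

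**The concern.** Each participant is tested with all three materials, so the order of testing is part of the design. Two things can go wrong. A material may be tested early more often than late (position), or it may more often follow one particular material (carry-over). Balancing position does not balance carry-over.

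Three materials give six ordered pairs of the form 'X directly before Y'. A list with three values, one fixed order per value, yields only three orders. If one earmold leaves a distinctive impression and is followed more often by A than by B, then A and B are judged against different backgrounds. Two earmolds that perform the same can then differ on average, and the planned t-test would report this as a material effect. For example, the control is made by a different route from the two printed earmolds. If it were the distinctive one, the resin-versus-PLA comparison would be exposed.

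**Working it through.** **Inputs from the documents.** Three arms, 1:1, defined by first material; a list of 3 × 10 = 30 places (Randomization). 90 earmolds at three each (Earmold Fabrication Period): 90 / 3 = 30 participants, which agrees with the list. Three test periods (Listening Session #02). Alpha .05 with Bonferroni (Analysis Plan); three pairs give .05 / 3 = .0167 per test, taken as two-sided.

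**Assumptions, because the documents give no figure.** Carry-over is first-order: λ_X is the shift that material X leaves on the next measurement. SD_d is the SD of the paired A minus B difference without carry-over, and σ is the within-participant error SD. A and B are identical and only C carries over, by 0.2, 0.3 or 0.45 SD_d.

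**Step 1: enumerate.** If each arm has one fixed order, there are two choices for the last two places in each arm, so 2³ = 8 sets. The two cyclic sets (ABC/BCA/CAB and ACB/BAC/CBA) cover 3 of the 6 ordered pairs. The other six sets cover 5 of 6. None covers all six. Only the cyclic sets balance position.

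**Step 2: bias.** In ABC/BCA/CAB, A follows C in two of three arms and B follows A in two of three. So

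bias(A − B) = (2/3)λ_C − (2/3)λ_A = (2/3)(λ_C − λ_A).

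In the non-cyclic sets, the third earmold's carry-over enters two of the three pairwise differences with coefficient ±1/3 and the remaining one with 0. For A versus B, four sets have ±1/3 and two have 0. A carry-over equal for all three materials cancels in every set.

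**Step 3: false-positive rate of the A-versus-B paired t-test** (n = 30, test at .0167, simulated):

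| Orders | Bias in SD_d, for λ_C = 0.2 / 0.3 / 0.45 SD_d | Rejection rate |
|---|---|---|
| 2 cyclic sets | 0.13 / 0.20 / 0.30 | about 4.4% / 8.6% / 18.7% |
| 4 non-cyclic sets | 0.07 / 0.10 / 0.15 | about 2.0–2.3% / 2.5–3.2% / 3.5–5.0% |
| 2 non-cyclic sets | 0 / 0 / 0 | at or below 1.7% |
| All six orders, 5 each | 0 / 0 / 0 | at or below 1.7% |

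The biases are λ_C × 2/3, λ_C × 1/3 and 0. Bias is shown as an absolute value; its sign depends on the set.

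**Step 4: what six orders do and do not remove.** Across all six orders each material directly follows each other material in 2 of 6, so

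bias(A − B) = (1/3)(λ_B + λ_C) − (1/3)(λ_A + λ_C) = (λ_B − λ_A)/3.

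C drops out. The remainder is zero when A and B carry over equally, but not otherwise.

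**Step 5: precision at n = 30.** The unadjusted variance of a pairwise difference is 2σ²/30 = 0.0667σ², for three orders or six. With participant, position, material and carry-over terms it is:

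- cyclic sets: 0.333σ²
- non-cyclic sets: 0.100–0.133σ², depending on the pair
- six orders: 0.083σ²

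Against six orders, the ratios are 0.333 / 0.083 = 4 for cyclic sets and 1.2 to 1.6 for non-cyclic ones. The adjusted standard error relative to the unadjusted one is √(0.333 / 0.0667) = 2.2 for a cyclic set and √(0.083 / 0.0667) = 1.1 for six orders.

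**The case against.** The strongest reply is that the text never states the sequences. It fixes only the first earmold and points to a workflow figure. If the second and third earmolds were alternated or randomised within each arm, all six orders may already be in use. That stands. A reader might infer that the design is unbalanced whatever the figure shows, or that the last two positions were not randomised at all. The documents support neither: they show only that no such allocation is described.

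A reader might also take 18.7% as this trial's error rate, or expect a four-fold gain from six orders. Both figures belong to the two cyclic sets, and nothing in the available text says that the order was cyclic. In the six other sets the effect on a given pair is small or absent, although those sets leave position unbalanced.

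The washout is no proof that carry-over was expected, because Listening Session #02 gives no reason for it. It is a mitigation and may work. Nor is every outcome equally exposed: one can see how a rating might be coloured by the earmold worn before, but it is harder to see how an acoustic measurement would be.

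Finally, the protocol is written in the past tense, so changing the list may no longer be possible. What remains after all this is that neither the randomisation as described nor the planned analysis protects against unequal carry-over, and a balanced alternative fits the same 30 participants.

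**Conclusion.** The point holds in conditional form. As described, randomisation settles only the first earmold, and the analysis ignores order. If each arm has one fixed order, predecessor balance is impossible with three orders. The consequence for two identical earmolds ranges from none to a false-positive rate of about 18.7% against a nominal 1.7%, depending on which of the eight sets was used and on an assumed carry-over of 0.2 to 0.45 SD_d.

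This rests on carry-over that survives the washout and differs between materials, and on three test periods per participant. It bears mainly on the perceptual ratings. It does not show that any result is biased. It shows that a balanced design was available with the same participants, earmolds and unadjusted precision.

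**What to change.** **If the list can still be changed.** In Randomization, replace the 1-to-3 list by a 1-to-6 list covering all six orders of EM_CTRL, EM_RES and EM_PLA, in permuted blocks of six. 30 = 5 × 6, so each order gets five participants and the first material still splits 10/10/10. Blocks of ten would have to go in any case, as ten is not divisible by six (or by three). If all six orders are already used equally within arms, no change of design is needed; state the rule in the text.

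**In the Analysis Plan.** Add a sensitivity analysis of the perceptual ratings with terms for position and preceding earmold. This is still useful with six orders, because the unadjusted A minus B keeps (λ_B − λ_A)/3.

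**If data are already collected.** Report the sequences actually used, with counts, and run the same sensitivity analysis where order was recorded. State its limit: under a cyclic order its standard error is about 2.2 times that of the unadjusted comparison, so a null adjusted result would be weak evidence.

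**Cost.** One regenerated list and one extra model; staff follow six orders instead of three. No extra participants, visits or earmolds.

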### Earmold Fabrication Period

After completing Listening Session #01, ear impressions were digitally scanned and edited using commercially available 3D editing software. The physical ear canal impression was then sent to a third-party earmold manufacturer. Each participant was made three earmolds, for an overall total of 90 earmolds. For each individual, one earmold was created using a *third-party* manufacturer with the traditional service delivery pathway and two earmolds were created *in-house* with the novel service-delivery pathway using local 3D printers. The *third-party* earmold served as the control earmold. The *in-house* earmolds were made from two different material-types and served as the study earmolds. To control for style of earmolds, all earmolds were made in a skeleton style with a sound bore that accommodates size #13T tubing and a separate select-a-vent (SAV).

### Listening Session #02

Once all earmolds were fabricated and received, participants were scheduled for Listening Session #02. This stage involved collecting objective acoustic measurements and subjective perceptual ratings while wearing each of the earmolds. A stock Unitron T-stride M behind-the-ear hearing aid was programmed to simulate a flat, mild, sensorineural hearing loss at

40 dB HL from octave frequencies between 250 to 8000Hz. The hearing aid was programmed and fit to NAL-NL2 targets for these threshold values. All advanced hearing aid programming and features were disabled. The same hearing aid was used across all participants. Participants underwent objective and subjective measures three times, once for the *third-party* control earmold and twice for each *in-house* study earmold. Each material-type condition was separated by a short 10 minute washout period, during which participants completed a self-assessment questionnaire.

## ANALYSIS PLAN

The alpha level of statistical significance was set at .05 for all statistical analyses. The main statistical analysis included a one-way, within group, repeated measures analysis of variance (RM-ANOVA) to compare the effect of 3D printed material across outcome measures. Assumption testing for normality, outliers, and sphericity were utilized. Outliers were assessed on an individual basis, using Cook's D and a strict cutoff of 0.5. Sphericity was evaluated using Mauchly's test for Sphericity with a criteria of .05. If sphericity was violated, then both Geisser & Greenhouse and Huynh Feldt correction factors were used, with the latter being used when epsilon was greater than .075. Pairwise t-tests with Bonferroni correction were used for planned comparisons.

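### Every outcome is tested at .05 with none named as confirmatory, so no identified claim carries the 5% level; Holm would also be a cheap gain over Bonferroni

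*Combined protocol and SAP*

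**What the plan says.** The Analysis Plan sets one level throughout: "The alpha level of statistical significance was set at .05 for all statistical analyses". Its main analysis is a one-way within-subject ANOVA used "to compare the effect of 3D printed material across outcome measures", so outcomes are plural and none is singled out. It adds: "Pairwise t-tests with Bonferroni correction were used for planned comparisons". It does not say which comparisons those are.

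Listening Session #02 describes the data as "collecting objective acoustic measurements and subjective perceptual ratings while wearing each of the earmolds" and adds: "Participants underwent objective and subjective measures three times". That establishes two kinds of outcome, but individual endpoints are neither listed nor ranked.

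Under Earmold Fabrication Period, the third-party earmold is the control and the in-house "earmolds were made from two different material-types and served as the study earmolds". This fits either two comparisons with control or all three pairs. The same section gives the size: "Each participant was made three earmolds, for an overall total of 90 earmolds".

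**The concern.** The plan names a main analysis but not a main outcome. It gives no testing order and no adjustment across outcomes. Its only multiplicity control, Bonferroni, is attached to the pairwise t-tests, and the natural reading is pairs of materials within one outcome. A material effect on whichever measure reaches p < .05 could therefore be presented as the trial's finding, and a reader could not tell which result had been protected at 5%.

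A smaller matter is power. Within one outcome, Bonferroni leaves some of the permitted error unspent, and with about 30 participants that costs power that could be recovered at almost no expense.

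**Working it through.** The plan has no power calculation, effect size or familywise error rate, so there is no stated figure to reproduce.

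**Inputs from the documents**
- Alpha: .05 per analysis (Analysis Plan). Sidedness is not stated; two-sided t-tests are assumed.
- Participants: 90 earmolds / 3 each = 30 (Earmold Fabrication Period). This agrees with the list length under Randomization, "This script randomly sequenced three blocks of ten numbers equally containing values from 1 to 3": 3 × 10 = 30.
- Conditions: three, all within participant.

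**Assumptions**
- Number of outcomes k: not given. k = 2 is the least the text supports.
- Correlation between outcomes: 0, 0.5 and 0.8.
- Effects: paired differences in SD units (SD of the paired difference = 1, equal correlations), 0.4 to 0.6 SD for both in-house materials.

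**Step 1. False findings across outcomes, no true effect**

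For independent outcomes the chance of at least one false omnibus result is 1 − 0.95^k.
- k = 1: 5.0%
- k = 2: 1 − 0.95² = 1 − 0.9025 = 9.75%
- k = 4: 1 − 0.8145 = 18.5%
- k = 6: 1 − 0.7351 = 26.5%

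For k = 2 with correlated outcomes (100,000 simulated null trials at each correlation, F on 2 and 58 df), the result is 9.26% at correlation 0.5 and 7.96% at 0.8. The rate falls back to 5% only if the outcomes are perfectly correlated. With one named outcome it is 5% by construction, however many exploratory outcomes sit beside it.

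**Step 2. Holm against Bonferroni within one outcome**

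Thresholds for three pairs: Bonferroni .05/3 = .0167 for each; Holm .0167, then .025, then .05. For two comparisons: Bonferroni .05/2 = .025 for each; Holm .025, then .05. Holm's first step equals Bonferroni's and its later steps are looser, so it rejects everything that Bonferroni rejects.

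With all materials equal, both methods give the same familywise error: 4.45% (three pairs) or 4.66% (two comparisons).

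Power to show both in-house earmolds different from control (200,000 simulated trials per scenario, n = 30):

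| Paired effect | Three pairs: Bonferroni → Holm | Two comparisons: Bonferroni → Holm |
|---|---|---|
| 0.4 SD | 21.6% → 27.0% | 27.3% → 37.8% |
| 0.5 SD | 41.6% → 48.7% | 48.9% → 60.8% |
| 0.6 SD | 63.9% → 70.7% | 70.7% → 80.4% |

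For two comparisons the chance of at least one detection is the same under both methods (80.4% at 0.5 SD). For three pairs it can rise, because rejecting resin against PLA relaxes the threshold for the control comparisons. With one material shifted +0.3 SD and the other −0.3 SD, the chance of at least one detection against control goes from 39.1% to 46.8%.

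The price is error that Bonferroni leaves unspent. With one in-house material truly shifted by 0.8 SD, the rate of false pairs rises from 1.65% to 4.66% (three pairs) or from 2.51% to 4.83% (two comparisons), still under 5%.

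**The case against.** The strongest reply is that nothing is invalid. Each test holds its 5% level, and acoustic and perceptual measures may answer separate questions that need no joint control. That stands as far as it goes: the 8% to 9.75% applies only if any significant outcome may serve as the trial's result. The plan does not say that outcomes are to be interpreted separately or as exploratory, though, and saying so would itself be a remedy.

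A reader might also infer that the plan lets either the omnibus test or a pairwise test carry a claim, which would raise the error further. The text does not support that: it ranks the ANOVA as the main analysis and the t-tests as planned comparisons.

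Nor do the documents give reason to demote the ANOVA in favour of the t-tests. That would reverse the plan's own ranking, and the effect on power depends on the undefined family. At 0.5 SD the omnibus test detects a material effect in 79.2% of simulated trials, against 75.0% for any of three Bonferroni pairs and 80.4% for either of two comparisons.

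Finally, Bonferroni is not an error. Choosing Holm is an improvement, not a correction.

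**Conclusion.** The point holds for the text available, from which the figures and an opening portion are absent. No confirmatory outcome and no rule across outcomes is given, and the family of planned comparisons is undefined. With two outcomes, the chance of at least one false omnibus finding is about 8% to 9.75%, depending on their correlation; it grows if there are more. The outcome count and correlations are assumptions.

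A reader might infer that the trial's primary claim has an inflated error rate. That goes too far, because the documents identify no such claim. The fault is that the 5% is not attached to one.

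The Holm gain is secondary: about 5 to 12 points of power to show both differences over the effects examined, all of which are assumed. This should be changed, but it does not undermine the individual tests.

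**What to change.** 1. Name one confirmatory outcome, keep the ANOVA already designated as the main analysis as its 5% test, and label all other outcomes exploratory. If a part of the document not available here already names one, carry it into the Analysis Plan.
2. State whether the planned comparisons are the two against control or all three pairs.
3. Optionally, replace Bonferroni with Holm for the planned paired t-tests within each outcome. This keeps the 5% familywise limit for that family.

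If outcome data have not been seen, the cost is SAP wording. The downsides are that the other outcomes lose confirmatory status, that Holm spends error that Bonferroni leaves unused, and that Holm has no simple matching simultaneous intervals, so Bonferroni intervals should be reported alongside.

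The document is written in the past tense, so data may already have been examined. In that case the choice of outcome and any switch to Holm must be disclosed as post hoc, or the results labelled exploratory. A choice made after seeing the results cannot restore the 5% guarantee.

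### The main RM-ANOVA has no term for test position: a trend over the session costs power if positions are balanced and biases the material contrasts if they are not

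*Combined protocol and SAP*

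**What the plan says.** The main model in the Analysis Plan is a "one-way, within group, repeated measures analysis of variance (RM-ANOVA) to compare the effect of 3D printed material across outcome measures", followed by comparisons of pairs: "Pairwise t-tests with Bonferroni correction were used for planned comparisons". For non-sphericity it says: "If sphericity was violated, then both Geisser & Greenhouse and Huynh Feldt correction factors were used". No position, order, sequence or period term is described.

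The design is organised by order. Under Randomization: "Participants were randomly assigned to one of three arms, using a 1:1 allocation ratio, each with a different initial material type". All participants then go on to the other two materials. Under Listening Session #02, the outcomes are "objective acoustic measurements and subjective perceptual ratings while wearing each of the earmolds", and the conditions follow one another: "Each material-type condition was separated by a short 10 minute washout period".

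The text does not say how the second and third materials were ordered. The figure captioned "Workflow study diagram across material-type groups" may show it, but it is missing from the extracted document, so this is not held against the plan.

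**The concern.** Ratings given three times in one sitting can drift through practice, fatigue or a shifting reference point. A one-way model has two places to put such a drift:

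- **Positions balanced over materials.** The material differences stay unbiased, but the drift inflates the error term. The test becomes conservative and misses real differences more often.
- **Positions unbalanced.** Part of the drift appears as a difference between materials. It can hide a true difference or create a false one, depending on its direction.

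Equal allocation of the first material balances position 1 only. It does not settle positions 2 and 3.

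**Working it through.** **Inputs from the documents.** "Each participant was made three earmolds, for an overall total of 90 earmolds" gives 90 / 3 = 30 participants, which agrees with the randomisation list of 3 blocks x 10. Alpha is .05. Three pairwise tests with Bonferroni give .05 / 3 = 1.67% each. The plan states no power, SD or effect size, so there is no figure of its own to reproduce.

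**Assumptions.** Within-subject SD 1 and sphericity; two-sided t-tests; both in-house molds 0.5 SD from control; a linear trend of d SD per position shared by all participants, with d = .25, .5 or 1; no carry-over. Listening Session #02 counts three rounds of measurement but also speaks of two for each in-house mold; this is read as three conditions.

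**1. No trend.** Material means 0, .5, .5 have grand mean 1/3. Squared deviations sum to 1/9 + 1/36 + 1/36 = 1/6, so the noncentrality is 30 x 1/6 = 5. Power is 48.2% on 58 error df (planned) and 48.1% on 56 (position added).

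**2. Balanced positions.** The trend's sum of squares is 30 x (d² + 0 + d²) = 60d². Left in the error term on 58 df, it multiplies error variance by 1 + 60d²/58 = 1.06, 1.26 and 2.03.

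**3. Unbalanced positions.** With one fixed sequence per arm there are 2 x 2 x 2 = 8 possible sets, of which only the two Latin squares balance all positions. This is a count of possibilities, not a probability. Take as an example CTRL-RES-PLA, RES-CTRL-PLA, PLA-CTRL-RES, 10 participants each. Mean positions are CTRL (1+2+2)/3 = 1.67, RES (2+1+3)/3 = 2.00 and PLA (3+3+1)/3 = 2.33. The PLA-CTRL contrast is biased by (2.33 - 1.67)d = 0.17, 0.33 and 0.67 SD.

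**4. Simulation**, 20,000 trials per setting (random order: 1,000 allocations x 40 trials). A repeat run agreed to within about one point.

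| Setting, planned analysis | d=.25 | d=.5 | d=1 | With position, any d |
|---|---|---|---|---|
| Balanced (six sequences x 5): type I error | 4.1% | 2.4% | 0.2% | 5.0-5.2% |
| Balanced: omnibus power | 45.1% | 35.9% | 13.1% | 47.8-48.2% |
| Balanced: control vs RES, paired t at 1.67% | 26.7% | 19.8% | 6.1% | 28.6-29.1% |
| Second and third molds random: type I error | 4.3% | 2.9% | 0.8% | 4.9-5.1% |
| Second and third molds random: omnibus power | 45.2% | 36.7% | 17.5% | 46.8-47.5% |
| Unbalanced example: type I error | 7.1% | 12.6% | 24.7% | 5.0-5.2% |
| Same, after planned sphericity correction | 7.1% | 12.4% | 23.5% | not applicable |
| Unbalanced example: power, trend opposing | 27.1% | 12.2% | 3.1% | 33.4-34.0% |
| Unbalanced example: power, trend adding | 66.3% | 77.8% | 89.4% | 33.4-34.0% |

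The switch between the two sphericity corrections was set at epsilon .75; the plan prints .075.

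**5. Sensitivity.** With one material 0.8 SD from the others and balanced positions, planned power falls from 89% to 87, 82 and 56%. A mild imbalance (Latin square, 12/9/9) biases the contrast between the materials with the most different mean positions by 0.2d = 0.05, 0.10 and 0.20 SD, but type I error stays below 5% (4.5, 3.1, 0.8%).

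**6. Does the remedy keep the sphericity protection?** With SDs .5/1/1.5 by material, no material effect, balanced positions and d=.5, the omnibus test with position rejects in 6.0% uncorrected and 5.2% with Mauchly's test and epsilon taken from its own residuals. The three pairwise contrasts (nominal 1.67%) reject in 0.1, 2.1 and 4.2% with one pooled error, 1.65, 1.69 and 1.67% when each position-adjusted difference has its own error, and 1.5, 1.7 and 1.6% with an unstructured joint model. The joint model used t on 27 df in place of Kenward-Roger and was not repeated.

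**The case against.** The harm rests on two things the documents do not give: a trend, and the order of the second and third molds. The largest error rates come from an order chosen for illustration, and they vanish if the missing figure shows a Latin square. With balanced or randomised order the planned test does not inflate type I error, and at d=.25 it loses only 3 points of power; d=1 means a 2 SD shift from first to third mold, which is extreme. Drift is implausible for the acoustic measures, which use one hearing aid with advanced features disabled. The plan's wording does not exclude further models. Adding position when positions are unbalanced and there is no trend costs more power than it saves in the mild balanced case.

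All of this is fair, and it limits the weight of the point. It does not remove it: order is what the trial randomises, no model that uses it is described, and under balance the correction is almost free. The cost under imbalance is the price of separating material from position, which the one-way model does not attempt.

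**Conclusion.** The concern holds. The missing position term is a fact of the stated plan; the damage is conditional. With no trend the planned test is valid. With a shared trend and balanced positions it is unbiased but conservative, losing about 3, 12 and 35 points of omnibus power at d = .25, .5 and 1. Bias and inflated type I error arise only if positions are materially unbalanced, which the text neither shows nor rules out. These sizes depend on the assumed 0.5 SD effect, a linear trend common to all participants and no carry-over. The point matters mainly for the subjective ratings. It should be addressed, but it does not by itself invalidate the analysis; confidence in its practical importance is medium.

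**What to change.** 1. Report the sequence used in each arm, all three positions, with the number of participants, or point to the figure if it is there.
2. If test order was recorded, add position (1-3) as a within-participant fixed effect beside material, at least for the subjective ratings.
3. Keep the protection against non-sphericity. For the omnibus test, take Mauchly's test and epsilon from the residuals of the model with position. Take the Bonferroni-adjusted contrasts from a model with unstructured within-participant covariance and Kenward-Roger df, not from one pooled error. If positions are balanced, position-adjusted paired differences, each with its own error on 30 - 3 = 27 df, do equally well.
4. Report the stated RM-ANOVA alongside, and label the adjusted analysis post hoc if data have been seen; the document is written in the past tense.
5. If order was not recorded, state that as a limitation.

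**Cost.** Plan wording and one variable. With balanced positions and no trend, omnibus power goes from 48.2% to 48.1% and paired contrasts from 28.8% to 28.7%. With unbalanced positions and no trend, omnibus power can fall from 48% to about 34%. In the example order the joint model takes control-RES from 29% to 23% and control-PLA from 29% to 14%; separate paired regressions would give 18% and 4%, so the joint model is preferable there. A position term does not remove carry-over between molds.
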